## **H. FOLLOW-UPS**

1. LI CONDUCTS A FOLLOW-UP EVALUATION VIA A TELEPHONE CALL AT 2 WEEKS.
  - a) TWO CALL ATTEMPTS ARE MADE.
2. LI CONDUCTS AN ADDITIONAL FOLLOW UP PHONE CALL CONDUCTED AT 12 WEEKS.
  - a) TWO CALL ATTEMPTS ARE MADE.
3. PATIENT IS ADVISED TO RETURN TO CLINIC AT 6 MONTHS FOR EVALUATION, LABS, PULMONARY FUNCTION, PULSE OXIMETRY AND SIX MINUTE WALK TEST.
  - a) IF RETURN TO CLINIC IS NOT POSSIBLE DUE TO DISTANCE, THE PATIENT IS ADVISED TO GO TO A LOCAL PHYSICIAN FOR EXAMINATION, LABS, PULMONARY FUNCTION, PULSE OXIMETRY, AND SIX-MINUTE WALK TEST AT 6 MONTHS.
  - b) TWO CALL ATTEMPTS ARE MADE TO OBTAIN PATIENT PROGRESS VIA A QUALITY OF LIFE SURVEY.

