## **5. HYPOTHESES**

### **5a. Primary Hypothesis/Quantitative Arm**

Null hypothesis: Following autologous stem cell treatment for chronic lung disease, patients will have no improvement in pulmonary function (measured by FEV1) at six months

Alternative hypothesis: Following autologous stem cell treatment for chronic lung disease, patients will have an increase in pulmonary function (measured by FEV1) of 5 to 10% or more

Rev\_2/5/16 Page 2 of 10

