**Research Protocol**  
**Lung Institute Dallas**

### **5b. Secondary Hypothesis/Quantitative Arm**

There will be no adverse events reported following autologous stem cell treatment for chronic lung disease.

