## 6. STUDY DESIGN

This study uses a concurrent mixed-methods approach to collect and analyze both qualitative and quantitative data. The *quantitative* arm will use a non-experimental, descriptive approach to measure and analyze pre- and post-stem cell treatment pulmonary function test results of treated patients. Measurement of the occurrence of adverse events will also be part of the quantitative arm.

Pre-treatment pulmonary function test results (measured by FEV1) will be compared with a six-month post-treatment pulmonary function test result (FEV1) for each patient. The aim of this method is to generalize an improvement in pulmonary function (measured by FEV1) among the general population of all individuals treated by autologous cell therapy for chronic lung disease.

The *qualitative* arm of the study uses an interpretive phenomenological approach to collect and analyze pre- and post- cell therapy anecdotal data regarding perceived quality of life among treated patients. Phenomenological research involves investigating the lived experience.

Qualitative research has several assumptions (D. Nicholls, 2009; Ritchie & Lewis, 2003). Primarily, there is no predetermined theoretical framework- rather the theory, if any, is derived from the data. Secondly, qualitative research is context-driven. Finally, qualitative researchers focus on the *emic* perspective that concerns itself with the view, perspectives and descriptions of others.

This study uses an *interpretive phenomenological analysis* (IPA) approach throughout the study from planning to data collection to analysis. This methodology is used to illuminate each participant's variation of the same general phenomenon (in this case, COPD) (Reissman, 2008; Ritchie & Lewis, 2003).

Data from both arms of the study will be combined following data collection for analysis, discussion and presentation. Safety data on adverse outcomes will be tracked and reported separately as a descriptive, quantitative analysis.

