**Research Protocol**  
**Lung Institute Dallas**

## 11. STUDY PROCEDURES

Informed Consent Form is obtained. Consent form must be complete, signed, and dated without forgeries or alterations. Information should be delivered in a manner in which the Patient and/or the patient's legal representative could reasonably be expected to understand.

A review of the patient's medical record will be conducted to approve for treatment. Approved treatment plans will be documented in the patient's electronic medical record. Medical records obtained from external providers will be kept in the patient's medical record and must include recent laboratory data, results of any outside office notes, chest x-ray results and any relevant information as required per treatment inclusions and exclusions protocol.

Prior to Bone Marrow aspiration, Adipose extraction, and Venous stem cell administration, the clinician will perform a physical assessment. Attached are the following Standard Operating Procedures (SOPs) for each type of cell therapy that Lung Institute provides to qualified candidates:

- Venous Procedure
- Adipose Extraction Procedure
- Bone Marrow Aspirate Procedure

Patient follow-up may be conducted at the Lung Institute facility or may be completed by telephone at 2 weeks, 3 months and 6 months post-treatment to measure adverse events and quality of life. Patient participation in these phone calls is voluntary. Data collected at these time points will be entered into password-protected database for data management and reporting. Patients will be issued a journal during their treatment to record quality of life indicators from the time they are discharged from the clinic until they are called for follow-up. This allows the patients to better recall how they felt/are feeling to better communicate progress during follow-up appointments/calls.

Patients will have pulmonary function testing 6 months post-treatment. This will be done at the Lung Institute facility, or by their primary care physician, or pulmonologist.

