## **12. STATISTICAL CONSIDERATIONS AND DATA ANALYSIS**

### **12a. Sample size**

The anticipated sample size for this study is two hundred patients.

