### **12b. Statistical methods**

For the quantitative, descriptive arm of this study, sample characteristics will be collected to include age, sex and diagnosis. Pre- and post-treatment FEV1 measurements will be collected on each patient and evaluated by simple measures of central tendency (mean, median and mode). Sufficient descriptive data will be collected and reported to encourage replication of our study.

For the qualitative, anecdotal arm of the study, Lung Institute utilizes CCQ, the Clinical COPD Questionnaire to document patient's perceptions on improved quality of life. The information will be collected and interpreted by evaluating for common themes within the anecdotes. As a note regarding the rigor of qualitative research: is important in qualitative research to ensure that the study is credible and trustworthy (Smith, Flowers and Larkin, 2009). A number of guidelines for assessing this quality look toward establishing credibility. Psychologist Lucy Yardley's work in 2000 provides the principles for assessing the quality of qualitative research and how the interpretive phenomenological method can address them. First, the study must provide good *sensitivity to context*. In this study, the immersion in the clinic through field experience, the existing literature on COPD and stem cell treatment, and the anecdotes obtained

Rev\_2/5/16 Page 7 of 10

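### Follow-up rests on voluntary calls and an advised six-month test, but the plan has no rule for unobserved patients, so completer-only results can mislead on benefit and harm

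*Combined protocol and SAP*

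**What the plan says.** **Collection.** Protocol Section 11 places follow-up for adverse events and quality of life at 2 weeks, 3 months and 6 months, at the facility or by telephone, and adds: "Patient participation in these phone calls is voluntary". CL-005 Part H provides for calls at 2 weeks and 12 weeks, and for each says "TWO CALL ATTEMPTS ARE MADE". It also sets two attempts at six months, described as being for a quality-of-life survey.

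**Six-month FEV1.** Section 11 states the test as something that will happen, at the clinic or with the patient's own physician. CL-005 Part H makes it advice: return to the clinic or, if distance prevents that, see a local physician.

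**Analysis.** Section 12b says: "Pre- and post-treatment FEV1 measurements will be collected on each patient", summarised by mean, median and mode. Section 6 says the pre-treatment value "will be compared with a six-month post-treatment pulmonary function test result (FEV1) for each patient", and aims to generalise to all individuals treated. The primary alternative in Section 5a is that "patients will have an increase in pulmonary function (measured by FEV1) of 5 to 10% or more". The secondary hypothesis in Section 5b is: "There will be no adverse events reported following autologous stem cell treatment for chronic lung disease". Section 12a gives the size without derivation or loss allowance: "The anticipated sample size for this study is two hundred patients".

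**Other safety route.** Section 11 requires all adverse events to go to the principal investigator and into the medical record.

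**The concern.** Collection is optional for the patient, while the analysis and the intended inference are written as if it were complete. The visible text does not say who is in the analysis, what the denominators are, how losses and deaths are reported, or what happens when a six-month value is absent.

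The patients have chronic lung disease, and the risks listed in Section 13 include stroke and possibly fatal pulmonary embolus. Those who die, are in hospital or are too ill to travel cannot easily return, be tested locally or take a call. All three research questions in Section 4 depend on these data. The safety hypothesis is the most exposed, because it concerns events reported: silence from unreached patients supports it as much as good health does.

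**Working it through.** **1. What can be reproduced.** The planned 200 cannot be re-derived, since no alpha, power, standard deviation or dropout rate is given. No loss rate appears either. Every missing share, return pattern and standard deviation below is an assumption.

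**2. Mean FEV1 change over all treated patients.** Let m be the share missing, C the completer mean and M the mean of the missing patients. The all-treated mean is (1 - m) × C + m × M. Take C = +5%, the lower end of the Section 5a target.

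| m | M = 0% | M = -5% |
|---|---|---|
| 10% | +4.5% | +4.0% |
| 20% | +4.0% | +3.0% |
| 30% | +3.5% | +2.0% |
| 40% | +3.0% | +1.0% |
| 50% | +2.5% | 0.0% |

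For example, 0.8 × 5 + 0.2 × (-5) = +3.0, and 0.6 × 5 + 0.4 × (-5) = +1.0. The value of M that brings the all-treated mean to zero is -5 × (1 - m)/m: -20% at m = 20%, and -7.5% at m = 40%.

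**3. Selection with paired data and no true mean change.** Suppose the chance of return follows a logistic function of the patient's own FEV1 change, the true mean change is zero and 60% return. If the odds of return rise 1.5-fold to 3-fold per standard deviation (SD) of better change, the completer mean is +0.16 to +0.35 SD. With an assumed SD of 15 percentage points that is +2.3 to +5.3 points. With 80% returning it is +0.08 to +0.19 SD, or +1.2 to +2.8 points. If return is unrelated to change the shift is zero. If the odds halve per SD of better change, so that worse patients return more, it is -0.25 SD at 60% returning. Pairing therefore does not remove selection, and the sign depends on who returns.

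**4. Zero adverse events.** The exact one-sided 95% upper limit with n patients observed and none with an event is 1 - 0.05^(1/n):

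- n = 200: 1.5%
- n = 140: 2.1%
- n = 100: 3.0%
- n = 50: 5.8%

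Each limit speaks for the unobserved patients only if they resemble those observed.

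**5. Choice of adverse-event denominator.** Assume a true rate of 10%, so 20 of 200 patients have an event.

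- Reach 40% of those 20 and 80% of the other 180: 8 cases among 8 + 144 = 152 patients with known status. The rate is 8/200 = 4.0% or 8/152 = 5.3%, both below 10%.
- Reach 70% of everyone: 14 cases among 140. The rate is 14/200 = 7.0% or 14/140 = 10.0%.

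Neither denominator is safe alone.

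**6. Quality of life.** Take the pilot's 84% (Section 2) as an illustrative rate among the 70% observed. The all-treated share then lies between 0.84 × 70 = 58.8% (no missing patient improved) and 58.8 + 30 = 88.8% (every missing patient improved).

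**The case against.** The study calls its quantitative arm non-experimental and descriptive, and several stronger readings fail.

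- A reader might infer from Section 12b that a baseline mean over all treated patients is set against a six-month mean over those who return, so that a gain could appear with nobody changing. Section 6 compares the two values for each patient, which points to paired change.
- A reader might infer that all outcomes come only from patients who answer a call. FEV1 cannot come from a call and may come from a local physician, follow-up may take place at the facility, and two attempts are made at each of three times. The statement that participation is voluntary concerns the calls.
- A reader might infer that a patient who dies or never answers is counted as free of events. No text says so. The plan is silent on denominators, and a death the clinic learns of would fall under the reporting rule in Section 11.
- A reader might infer that bias in favour of treatment is certain. No return rate or pattern is given, and step 3 yields zero or reversed bias under other patterns.

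These points limit the claim but do not answer it. The reporting rule in Section 11 deals with events once known; it does not seek them in patients who cannot be reached. CL-005 Part E refers to an incident-reporting policy that is not among the documents. The descriptive label sits beside a null and an alternative hypothesis and a stated aim to generalise, and a descriptive mean still needs a stated denominator.

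**Conclusion.** The point holds as a gap in the analysis plan with a probable, but not demonstrated, direction. Followed as written, the plan yields a completer-only result with no qualification and lets an absence of reports support the safety hypothesis. That completeness is assumed is an inference from Section 12b's wording, not a stated rule.

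The size depends on loss rates the documents do not give. Under the assumed inputs, a +5% completer result corresponds to +3% or +1% over all treated patients at 20% or 40% missing, and selection alone can reach about 5 points at the strong end of step 3. The upper limit for zero events doubles from 1.5% to 3.0% if half of 200 are observed. The sponsor should correct this before analysis.

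**What to change.** In Section 12b:

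- (a) Report the numbers treated, dead, lost and analysed at each time point. State that FEV1 and CCQ change is computed within patients, as Section 6 implies for FEV1.
- (b) Compare baseline FEV1, age and diagnosis between completers and non-completers.
- (c) Add a sensitivity analysis over all treated patients that gives non-completers zero or negative change. Unless the main conclusion holds there, limit it to patients observed.
- (d) Report adverse events over all treated patients and over those with known status, with an exact upper confidence limit. List status-unknown patients separately, and do not treat none reported as none occurred.
- (e) Before coding a patient lost, check the medical record and the emergency contact. The Office Manager SOP already collects that contact, and Section 11f says full contact information is retained.

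Section 11 and CL-005 Part H must also be reconciled on two points: whether the six-month test is required or advised, and whether six-month follow-up by telephone covers adverse events or only the quality-of-life survey.

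The cost is wording, a few tables and some staff time on records already held. The reported result may be less favourable.

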### **ATTACHMENT(S):**

**A-1:** VENOUS PROCEDURE (CLINICAL - SOP)

**A-2:** BONE MARROW ASPIRATE PROCEDURE (CLINICAL - SOP)

**A-3:** DISCHARGE TREATMENT DAY PROCEDURE (CLINICAL-

**SOP) A-4:** OFFICE MANAGER PROCEDURE (CLINICAL-SOP)

**STATUTORY REFERENCE(S):**

**CONTRACT REFERENCE(S):**

**ELEMENT REFERENCE(S):**

**RELATED POLICY(S):**

10Mar2016 - version 2.0

LI-001

Lung Institute Clinical Procedure	Standard Operating Procedure (SOP) Venous Procedure
Issue Date: Last Revision Date: Owner: Document Author: Approved By:	11/20/2015 3/8/2016 Clinical Department [name], ARNP – Lung Institute Operations Medical Director
Purpose:	To outline the clinical Venous Procedure; to ensure Patient and employee safety and minimize risk of exposure or incident.
Primary User: Other department(s) Affected:	LI-Clinical Department RMS-Records Department
Systems Used:	EMR; ZOHO

These instructions encompass the process for the preparation and completion of the A-ASC Venous Procedure treatment days. Steps must be completed in sequential order unless instructed to skip steps in the procedure work flow.

1.	Is today the first treatment day for the Patient? ➤ If NO > Proceed to Step 6 of this SOP ➤ If YES > Proceed to Step 2 of this SOP
-----------	--

2.	
Has the Practitioner reviewed the required records prior to procedure and completed the required Pre-Op evaluation and documentation?
 
 
• Signed Patient Consent Form
 
• Patient Diagnostics: 
 
Within 6 months from first DOS (Date of Service) is Preferred for Venous & 3 months for Bone Marrow
 
✓ Labs 
 
a) Complete Blood Count with Differential (CBC w/ Diff)
 
b) Comprehensive Metabolic Panel (CMP) - Basic Metabolic Panel (BMP) may be acceptable
 
c) For Bone Marrow Only: Prothrombin Time-International Normalized Ratio (PT-INR)
 
 
 
✓ Diagnostic Imaging/Testing 
 
a) Chest X-Ray; or
 
b) CT Scan of Chest
 
c) For Bone Marrow Only: EKG
 
 
 
 
 
• Patient History: 
 
✓ Previous Serious Illness;
 
✓ Current and Chronic Illness;
 
✓ Surgical History; and
 
✓ Treating Physician Reports
 
 
 
• Allergies 
 
✓ If Allergies Present - MUST use Suitable Alternative(s): 
 
a) Latex Allergy - Non-Latex Gloves
 
b) Betadine Allergy – Use Chlorhexidine
 
c) Antibiotics Allergy - If allergic to Penicillin use Lincocin
 
d) Lidocaine Allergy - Use Marcaine or Diphenhydramine
 
e) Medication Allergies - Use suitable substitutes
 
 
 
 
 
• Medications 
 
✓ If Patient is on Blood Thinners or Anti-arrhythmics – Patient is only Suitable for Venous TX
 
 
 
• Bleeding Tendencies
 
 
➤ If NO > Assess missing documentation and obtain prior to moving forward with procedure.

-----------	--

10Mar2016 - version 2.0

LI-001

	
➤ If YES > Proceed to Step 3 of this SOP

3.	
Has the Clinic Staff properly disposed of all materials associated with previous Patients and thoroughly cleaned all surface areas with Caviwipes per disinfection protocols?
 
➤ If NO > Procedure Room must be cleaned per protocols prior to proceeding.
 
➤ If YES > Proceed to Step 4 of this SOP

4.	
Clinic Staff must properly prepare and label syringes and supplies for Patient procedure.
 
 
• Has the Clinic Staff completed the following in the lab area? 
 
✓ Open Harvest PRP (PC-60) Kit;
 
✓ Label syringes and supplies w/ Patient Name and D/O/B;
 
✓ Draws 8ml ACD-A into 60ml syringe;
 
✓ Transfer 2ml ACD-A from syringe into white port of Process Disposable (PD) Cup; and
 
✓ Spike 100ml normal saline IV bag with 15ggt IV tubing.
 
 
 
 
➤ If NO > Step must be completed prior to proceeding.
 
➤ If YES > Proceed to Step 5 of this SOP

5.	
Clinic Staff must properly prepare mayo stand under a clean technique for Patient procedure.
 
 
• Has the Clinic Staff prepared the mayo stand by covering with underpad and ensuring all the following is made available? 
 
✓ 60ml Syringe with ACD-A
 
✓ 20g or 22g IV Catheter
 
✓ Alcohol Prep Pad(s)
 
✓ 2x2 Gauze
 
✓ IV Starter Kit
 
 
 
• Has the Clinic Staff hung the IV bag in the exam room on the IV pole? 
 
✓ Previously spiked 100ml Normal Saline (NS) IV Bag
 
 
 
 
➤ If NO > Preparation is required prior to proceeding.  ➤ If YES > Proceed to Step 9 of this SOP

6.	
Has the Clinic Staff properly disposed of all materials associated with previous Patients and thoroughly cleaned all surface areas with Caviwipes per disinfection protocols?
 
➤ If NO > Procedure Room must be cleaned per protocols prior to proceeding.  ➤ If YES > Proceed to Step 7 of this SOP

7.	
Clinic Staff must properly prepare and label syringes and supplies for Patient procedure.
 
 
• Has the Clinic Staff completed the following in the lab area? 
 
✓ Open Harvest PRP (PC-30) Kit;
 
✓ Label syringes and supplies w/ Patient Name and D/O/B;
 
✓ Draws 6ml ACD-A into 30ml syringe;
 
✓ Transfer 2ml ACD-A from syringe into white port of Process Disposable (PD) Cup; and
 
✓ Spike 100ml normal saline IV bag with 15ggt IV tubing.
 
 
 
 
➤ If NO > Step must be completed prior to proceeding.  ➤ If YES > Proceed to Step 8 of this SOP

10Mar2016 - version 2.0

LI-001

8.	
Clinic Staff must properly prepare mayo stand under a clean technique for Patient procedure.
 
 
• Has the Clinic Staff prepared the mayo stand by covering with underpad and ensuring all the following is made available? 
 
✓ 35ml Syringe with ACD-A
 
✓ 20g or 22g IV Catheter
 
✓ Alcohol Prep Pad(s)
 
✓ 2x2 Gauze
 
✓ IV Starter Kit
 
 
 
• Has the Clinic Staff hung the IV bag in the exam room on the IV pole? 
 
✓ Previously spiked 100ml Normal Saline (NS) IV Bag
 
 
 
 
➤ If NO > Preparation is required prior to proceeding.  ➤ If YES > Proceed to Step 9 of this SOP

9.	
Clinic Staff assumes responsibility of Patient and Patient care from the Office Manager.
 
 
• If Patient is on O, has Patient been transferred to clinic's oxygen concentrator for the remainder of the day's visit?
 
 
➤ If applicable, and NO > Transfer Patient as required prior to moving forward with SOP.  ➤ If not applicable; or applicable, and YES > Proceed to Step 10 of this SOP


10.
	
Clinic Staff conducts introductions, reviews process, and checks for Patient readiness.
 
 
• Has Clinic Staff introduced themselves? 
 
✓ Name and Roles
 
 
 
• Has Clinic Staff reviewed the procedure process for the day? 
 
✓ Go over what the Patient can expect during the days procedure
 
 
 
• Has Clinic Staff ensured Patient readiness? 
 
✓ Answer any questions the Patient may have; and
 
✓ Check to see if Patient needs to use the restroom prior to procedure.
 
 
 
 
➤ If NO > Step must be completed prior to proceeding.
 
➤ If YES > Proceed to Step 11 of this SOP

11.
	
Clinic Staff obtains vitals.
 
 
• Has Clinic Staff obtained the following vitals? 
 
✓ Blood Pressure;
 
✓ Pulse;
 
✓ Heart Rate;
 
✓ Respiratory Levels;
 
✓ SaO Levels;
 
✓ EKG (If required, per Practitioner's judgement); and
 
✓ PFT (May be obtained within the 3 days of scheduled treatment)
 
 
 
 
➤ If NO > Obtaining Patient vitals is required prior to proceeding.
 
➤ If YES > Proceed to Step 12 of this SOP

12.
	
Clinic Staff completed the subjective/chief complaint.
 
 
• Has Clinic Staff completed the Subjective/Chief Complaint? 
 
✓ Patient Complaint/Primary Reason for Visit (i.e.: Patient here for shortness of breath, second day of procedure, COPD Treatment, etc.)
 
 
 
 
➤ If NO > Step must be completed prior to proceeding.
 
➤ If YES > Proceed to Step 13 of this SOP

10Mar2016 - version 2.0

LI-001

13.
	
Is today the first treatment day for the Patient?
 
➤ If NO > Proceed to Step 16 of this SOP
 
➤ If YES > Proceed to Step 14 of this SOP


14.
	
Clinic Staff completed initial evaluation, including medical history.
 
 
• Has Clinic Staff completed the following Patient History? 
 
✓ Patient Complaint/Primary Reason for Visit
 
✓ Social;
 
✓ Medical;
 
✓ Allergies;
 
✓ Medications;
 
✓ Surgical;
 
✓ Family; and
 
✓ Review of Systems
 
 
 
 
➤ If NO > Step must be completed prior to proceeding.
 
➤ If YES > Proceed to Step 15 of this SOP

15.	
Clinic Staff draws blood and affixes IV line to catheter.
 
 
• Has Clinic Staff completed the following? 
 
✓ IV site is prepped and disinfected;
 
✓ Affix tourniquet to upper arm;
 
✓ Insert IV catheter into desired site;
 
✓ Remove needle from catheter;
 
✓ Affix Harvest PRP kit 60ml syringe to catheter and draw approximately 55ml of blood;
 
✓ Remove syringe and affix IV drip line to catheter;
 
✓ Wrap with Coban bandage to hold catheter in place;
 
✓ Check the patency and flow to make sure it is correct;
 
✓ Once correct, close off IV drip line until reinfusion; and
 
✓ Dispose of supplies in designated biohazard/sharps containers.
 
 
 
 
➤ If NO > Step must be completed prior to proceeding.
 
➤ If YES > Proceed to Step 17 of this SOP

16.	
Clinic Staff draws blood and affixes IV line to catheter.
 
 
• Has Clinic Staff completed the following? 
 
✓ IV site is prepped and disinfected;
 
✓ Affix tourniquet to upper arm;
 
✓ Insert IV catheter into desired site;
 
✓ Remove needle from catheter;
 
✓ Affix Harvest PRP kit 35ml syringe to catheter and draw approximately 30ml of blood;
 
✓ Remove syringe and affix IV drip line to catheter;
 
✓ Wrap with Coban bandage to hold catheter in place;
 
✓ Check the patency and flow to make sure it is correct;
 
✓ Once correct, close off IV drip line until reinfusion; and
 
✓ Dispose of supplies in designated biohazard/sharps containers.
 
 
 
 
➤ If NO > Step must be completed prior to proceeding.
 
➤ If YES > Proceed to Step 17 of this SOP

10Mar2016 - version 2.0

LI-001

17.	
Clinic Staff takes blood supply to lab for processing and notifies Practitioner of Patient readiness.
 
 
• Has Clinic Staff completed the following? 
 
✓ Notified Practitioner of Patient readiness;
 
✓ Transfer blood drawn to the correctly labeled Harvest PRP cup for centrifuging; and
 
✓ Place PD Cup in centrifuge and press green start button or PRP start button.
 
 
 
 
➤ If NO > Step must be completed prior to proceeding.
 
➤ If YES > Proceed to Step 18 of this SOP

18.	
Practitioner reviews and conducts required pre-procedural protocols and renders physical exam.
 
 
• Has Practitioner reviewed the following prior to procedure and conducted the required? 
 
✓ Has Practitioner conducted and noted H&P or SOAP (Subjective; Objective; Assessment; Plan) on the Patient record; and
 
✓ Reviewed all required pre-procedural documentation?
 
 
 
 
➤ If NO > Step must be completed prior to moving forward with procedure.
 
➤ If YES > Proceed to Step 19 of this SOP

19.	
Clinic Staff will extract venous final product.
 
 
• Has Clinic Staff completed the following? 
 
✓ Draw PRP from the side compartment of PRP cup, identified by the white port.
 
✓ Use PRP to wash walls of PD Cup at least twice; and
 
✓ Extract into a 20ml syringe
 
 
 
 
➤ If NO > Step must be completed prior to proceeding.
 
➤ If YES > Proceed to Step 20 of this SOP

20.	
Clinic Staff administers final product.
 
 
• Has Clinic Staff completed the following? 
 
✓ Place venous final product (injected via the 20ml syringe referenced above) into the IV bag; and
 
✓ Open IV line (checking for sufficient flow and drip rate)
 
 
 
 
➤ If NO > Step must be completed prior to proceeding.
 
➤ If YES > Proceed to Step 21 of this SOP

21.	
Clinic Staff conducts on-going oversight of Patient during administration.
 
 
• Has Clinic Staff confirmed the patency and flow are correct?
 
 
➤ If NO > Step must be completed prior to proceeding.
 
➤ If YES > Proceed to Step 22 of this SOP

22.	
Clinic Staff starts nebulizer treatment.
 
 
• Has Clinic Staff completed the following? 
 
✓ Place glutathione and saline into nebulizer medicine cup and provide Patient with instructions to begin nebulizing treatment; and
 
 
 
 
➤ If NO > Step must be completed prior to proceeding.
 
➤ If YES > Proceed to Step 23 of this SOP

10Mar2016 - version 2.0

LI-001

23.	
Clinic Staff discontinues IV line and nebulizer; and provide post care instructions.
 
 
• Has the Clinic Staff completed the following? 
 
✓ Turn off nebulizer when treatment completed;
 
✓ When final product has emptied IV bag, use normal saline flush to flush entire contents of IV line;
 
✓ Remove IV catheter;
 
✓ Place 2x2 gauze pad over site, affix coban bandage;
 
✓ Instruct Patient to remove gauze and coban after 20 to 30 minutes; and
 
✓ Dispose of supplies in designated biohazard containers.
 
 
 
 
➤ If NO > Step must be completed prior to proceeding.
 
➤ If YES > Proceed to Step 24 of this SOP

-----	---

24.	
Has Clinic Staff provides Patient with discharge folder and post-care instructions and answered any Patient questions or concerns?
 
 
• Has Clinic Staff advised the Patient of the below post-care instructions and ensured that they understand said instructions; answering any questions or concerns? 
 
✓ Briefly review and explain the discharge folder contents to Patient;
 
✓ Review LI follow-up procedures; and
 
✓ Review Patient Journals for quality of life outcome data.
 
 
 
 
➤ If NO > Step must be completed prior to proceeding.  ➤ If YES > Proceed to Step 25 of this SOP

25.	
Has Clinic Staff updated EMR as required?
 
 
• Capture procedure as required in the EMR: 
 
✓ Vitals
 
✓ Testing Conducted
 
✓ Medications Administered
 
✓ Lot Numbers and expirations (As Applicable);
 
✓ Dosage(s)
 
✓ Site(s) of Procedure and/or Administrations (Left vs Right, and location)
 
✓ Route (PO, SubQ, IM, IV, Etc.); and
 
✓ Any additional notation or documentation required (e.g.: Checklists and/or Flowsheets).
 
 
 
 
➤ If NO > Step must be completed to complete SOP.  ➤ If YES > SOP Complete

Notes:	
Related Documents: P&P CL-005	

Lung Institute  Clinical Procedure
	
Standard Operating Procedure (SOP)  Bone Marrow Aspirate Procedure

Issue Date: 11/20/2015  Last Revision Date: 3/7/2016  Owner: Clinical Department  Document Author: [name], ARNP – Lung Institute Operations  Approved By: Medical Director
	

Purpose:
	
To outline the clinical treatment day for the Bone Marrow Aspirate Procedure; to ensure Patient and employee safety and minimize risk of exposure or incident.

Primary User:  Other department(s) Affected:
	
LI-Clinical Department  RMS-Records Department

Systems Used:
	
EMR; ZOHO

These instructions encompass the process for the preparation and completion of the A-ASC Bone Marrow Procedure treatment day. Steps must be completed in sequential order unless instructed to skip steps in the procedure work flow.

1.	
Is today the first treatment day for the Patient?
 
 
➤ If NO > Proceed to Step 3 of this SOP
 
➤ If YES > Proceed to Step 2 of this SOP
 

2.	
Has the Practitioner reviewed the required records prior to procedure and completed the required Pre-Op evaluation and documentation?
 
 
• Signed Patient Consent Form
 
• Patient Diagnostics: Obtained within 3 months from first DOS (Date of Service) is Preferred 
 
✓ Labs 
 
a) Complete Blood Count with Differential (CBC w/ Diff)
 
b) Comprehensive Metabolic Panel (CMP) - Basic Metabolic Panel (BMP) may be acceptable
 
c) Prothrombin Time-International Normalized Ratio (PT-INR)
 
 
 
✓ Diagnostic Imaging/Testing 
 
a) Chest X-Ray; or
 
b) CT Scan of Chest
 
c) EKG
 
 
 
 
 
• Patient History: 
 
✓ Previous Serious Illness;
 
✓ Current and Chronic Illness;
 
✓ Surgical History; and
 
✓ Treating Physician Reports
 
 
 
• Allergies 
 
✓ If Allergies Present - MUST use Suitable Alternative(s): 
 
a) Latex Allergy - Non-Latex Gloves
 
b) Betadine Allergy – Use Chlorhexidine
 
c) Antibiotics Allergy - If allergic to Penicillin use Lincocin
 
d) Lidocaine Allergy - Use Marcaine/Bupivacaine or Diphenhydramine
 
e) Medication Allergies - Use suitable substitutes
 
 
 
 
 
• Medications 
 
✓ If Patient is on Blood Thinners or Anti-arrhythmics – Patient is only Suitable for Venous TX
 
 
 

10Mar2016 - version 2.0

LI-001

	
 
• Bleeding Tendencies
 
➤ If NO > Assess missing documentation and obtain prior to moving forward with procedure.
 
➤ If YES > Proceed to Step 3 of this SOP
 

3.	
Has the Clinic Staff properly disposed of all materials associated with previous Patients and thoroughly cleaned all surface areas with Caviwipes per disinfection protocols?
 
 
➤ If NO > Procedure Room must be cleaned per protocols prior to proceeding.
 
➤ If YES > Proceed to Step 4 of this SOP
 

4.	
Clinic Staff must properly prepare and label syringes and supplies for Patient procedure.
 
 
• Has the Clinic Staff completed the following in the lab area? 
 
✓ Open Harvest PRP (PC-60) Kit;
 
✓ Label syringes and supplies w/ Patient Name and D/O/B;
 
✓ Draws 8ml ACD-A into 60ml syringe; and
 
✓ Spike 100ml IV bag with filter tubing to be used for administration of final product.
 
 
 
 
➤ If NO > Preparation is required prior to proceeding.
 
➤ If YES > Proceed to Step 5 of this SOP

5.	
Clinic Staff must properly prepare mayo stand under aseptic technique for Patient Bone Marrow procedure.
 
 
• Has the Clinic Staff prepared the mayo stand and procedure room with Harvest BMAC kit and by ensuring all the following is made available? 
 
✓ Harvest BMAC kit
 
✓ Marcaine/Bupivacaine 0.25%
 
✓ Heparin 1,000units/ml
 
✓ Anesthesia Syringe
 
 
 
 
➤ If NO > Preparation is required prior to proceeding.
 
➤ If YES > Proceed to Step 6 of this SOP

6.	
Clinic Staff must properly prepare mayo stand under a clean technique for Patient Venous procedure.
 
 
• Has the Clinic Staff prepared the mayo stand by covering with underpad and ensuring all the following is made available? 
 
✓ 60ml Syringe with ACD-A
 
✓ 20g or 22g IV Catheter
 
✓ IV Catheter Hep-Lock
 
✓ Alcohol Prep Pad(s)
 
✓ 2x2 Gauze
 
✓ IV Starter Kit
 
 
 
 
➤ If NO > Preparation is required prior to proceeding.
 
➤ If YES > Proceed to Step 7 of this SOP

7.	
Clinic Staff assumes responsibility of Patient and Patient care from the Office Manager.
 
 
• If Patient is on O, has Patient been transferred to clinic's oxygen concentrator for the remainder of the day's visit?
 
 
➤ If applicable, and NO > Transfer Patient as required prior to moving forward with SOP.
 
➤ If not applicable; or applicable, and YES > Proceed to Step 8 of this SOP

8.	
Has Clinic Staff conducted introductions, review process, and checks for readiness?
 
 
• Clinic Staff introduces themselves; 
 
✓ Name and Roles
 
 
 
• Reviews the procedure process for the day; and 
 
✓ Go over what the Patient can expect during the days procedure
 
 
 
• Ensure Patient readiness 
 
✓ Answer any questions the Patient may have; and
 
✓ Check to see if Patient needs to use the restroom prior to procedure.
 
 
 
 
➤ If NO > Preparation is required prior to proceeding.
 
➤ If YES > Proceed to Step 9 of this SOP

9.	
Clinic Staff obtains vitals.
 
 
• Has the Clinic Staff obtained Patient Vitals? 
 
✓ Blood Pressure;
 
✓ Pulse;
 
✓ Heart Rate;
 
✓ Respiratory Levels;
 
✓ SaO Levels;
 
✓ EKG (Required to be obtained prior to Bone Marrow Procedure); and
 
✓ PFT (May be obtained within the 3 days of scheduled treatment)
 
 
 
 
➤ If NO > Obtaining Patient vitals is required prior to proceeding.
 
➤ If YES > Proceed to Step 10 of this SOP

10.	
Clinic Staff completed the subjective/chief complaint.
 
 
• Has Clinic Staff completed the Subjective/Chief Complaint? 
 
✓ Patient Complaint/Primary Reason for Visit (i.e.: Patient here for shortness of breath, second day of procedure, COPD Treatment, etc.)
 
 
 
 
➤ If NO > Step must be completed prior to proceeding.
 
➤ If YES > Proceed to Step 11 of this SOP

11.	
Is today the first treatment day for the Patient?
 
➤ If NO > Proceed to Step 13 of this SOP
 
➤ If YES > Proceed to Step 12 of this SOP

12.	
Clinic Staff completed initial evaluation, including medical history.
 
 
• Has Clinic Staff completed the following Patient History? 
 
✓ Patient Complaint/Primary Reason for Visit
 
✓ Social;
 
✓ Medical;
 
✓ Allergies
 
✓ Surgical;
 
✓ Family; and
 
✓ Review of Systems
 
 
 
 
➤ If NO > Step must be completed prior to proceeding.
 
➤ If YES > Proceed to Step 13 of this SOP

13.	
Clinic Staff draws blood and affixes Hep-lock to catheter.
 
 
• Has Clinic Staff completed the following? 
 
✓ IV site is prepped and disinfected;
 
✓ Apply tourniquet to upper arm;
 
✓ Insert IV catheter into desired site;
 
✓ Remove needle from catheter;
 
✓ Affix Harvest PRP kit 60ml syringe to catheter and draw approximately 60ml of blood;
 
✓ Remove syringe and affix Hep-lock to catheter;
 
✓ Flush with Heparin syringe;
 
✓ Wrap with Coban bandage to hold catheter in place; and
 
✓ Dispose of supplies in designated biohazard/sharps containers.
 
 
 
 
➤ If NO > Step must be completed prior to proceeding.
 
➤ If YES > Proceed to Step 14 of this SOP

14.	
Clinic Staff takes blood sample to lab to processing and notifies Practitioner of Patient readiness.
 
 
• Has Clinic Staff processed blood in lab as required? 
 
✓ Notified Practitioner of Patient readiness;
 
✓ Transfer blood drawn to the correctly labeled Harvest PRP cup into the red port for centrifuging;
 
✓ Place PD Cup in centrifuge and press green start button or PRP start button; and
 
✓ Verify centrifuge is running properly.
 
 
 
 
➤ If NO > Step must be completed prior to proceeding.
 
➤ If YES > Proceed to Step 15 of this SOP

15.	
Practitioner reviews and conducts required pre-procedural protocols and renders physical exam.
 
 
• Has Practitioner reviewed the following prior to procedure and conducted the required? 
 
✓ Has Practitioner conducted and noted H&P or SOAP (Subjective; Objective; Assessment; Plan) on the Patient record; and
 
✓ Reviewed all required pre-procedural documentation?
 
 
 
 
➤ If NO > Step must be completed prior to moving forward with procedure.
 
➤ If YES > Proceed to Step 16 of this SOP

16.	
Clinic Staff will extract venous final product.
 
 
• Has Clinic Staff completed the following? 
 
✓ Remove approximately 10-15ml plasma from white port of PD Cup using Harvest kit syringe with yellow stoppers and discard to appropriate biohazard container;
 
✓ Draw PRP from the side compartment of PRP cup, identified by the white port.
 
✓ Use PRP to wash walls of PD Cup at least twice; and
 
✓ Extract into a 20ml syringe and place labeled syringe on top of clean box for re-infusion once bone marrow extraction is complete.
 
 
 
 
➤ If NO > Step must be completed prior to proceeding.
 
➤ If YES > Proceed to Step 17 of this SOP

MATERIAL	Amount Required
BMAC Harvest kit (BMAC – 60-07)	1

17.
	
Has Practitioner ensured all of the following Reagents and Materials availability and prepare for procedure?
 
 
• Has Practitioner washed hands according to hand washing hygiene protocol?
 
• Has Practitioner dressed in appropriate PPE (Personal Protective Equipment)? 
 
✓ Gown
 
✓ Shoe Covers
 
✓ Hair/Head Cover
 
✓ Mask
 
✓ Gloves (to be donned upon right before commencement of procedure)
 
 
 
• Has Practitioner ensured all of the following Reagents and Materials availability and prepare lab space for procedure?
 
 
REAGENTS:
 
 
✓ Marcaine/Bupivacaine 0.25%
 
✓ Heparin 1,000units/ml
 
 
MATERIALS:
 
➤ If NO > Materials required must be available and prepared prior to proceeding.
 
➤ If YES > Proceed to Step 18 of this SOP

